6.4. Concomitant Therapy (if applicable)

New diagnosis and initiation of a new therapeutic including supplements during the course of the study should be disclosed. Antibiotic treatment during the course of the study will lead to discontinuation.

6.5. Rescue Medications and Procedures (if applicable)

N/A

6.6. Compliance Checks

Participant adherence will be monitored weekly via email and/or text messages through self-reporting of number of treatment pouches left.

6.7. Withdrawal / Discontinuation of Enrolled Participants

At baseline and every week after for the duration of the study, participant will answer a 33 question gastrointestinal symptom assessment with the PROMIS Gastrointestinal Symptom Scale (Spiegel, et al, Am J Gastrol, 2014). If a subject experience and increase in 2 levels over baseline in their response to questions 2 (abdominal pain), 6 (abdominal discomfort), 8 (constipation), 16 (diarrhea), 22 (abdominal distention), 26 (abdominal bloating), 31 (nausea), or 33 (vomiting) on the PROMIS Gastrointestinal Symptom Scale, they will be a) withdrawn from the study if the participant is in the first 10 days of their participation, or b) asked to go back to the lower dose of 5g sachets twice daily and reassessed in 3 days, if the participant has passed day 10 of participation. If participants are able to tolerate the lower dose, they will continue participating in the trial albeit consuming the lower dose of the prebiotic treatment. Likewise, if a participant develops a condition that is an exclusion criterion or participant noncompliance increases risk of decreased study integrity, the participant will be withdrawn from the study.

If 5 of the first 20 subjects enrolled experience a change of 2 levels on questions 2, 6, 8, 16, 22, 26, 31, 33 on the PROMIS Gastrointestinal Symptom Scale (bloating, flatulence, watery stools, abdominal pain) compared to baseline or higher adverse event leading to subject discontinuation, we will stop the study temporarily and request the medical monitor to do an unblinded assessment of the data. The medical monitor (unblinded) will assess subjects who discontinued due to the specified adverse effects to determine if they are all in one arm of the study or range across arms. The medical monitor will assess if there is a safety signal in a specific arm or treatment dose over the other that warrants the closure of the study. Since the medical monitor will be the person determining continuation or discontinuation of the study, the study team will remain blinded and unbiased.

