Where the K_m factor is a number based on body surface area. In our animal study we used a dose of 1,500 mg kg⁻¹, based on ~30 mg LacNAc fed to a ~20 g mouse per day²⁵. We used a K_m factor of 3 for mice and 37 to represent a 60 kg human adult.

We can consistently produce hGOS containing concentrations that exceed 25 g/L of LacNAc with no significant variation between batches observed. Therefore, our approach is to normalize to reach the proposed dose levels using pure GOS. The active component is in power form that will be obtained after lyophilization. Concentration will be confirmed using previously developed HPLC protocols³³

Acquisition: [name], Professor of Plant and Microbial Biology at North Carolina State University and Co-investigator in this proposal, will coordinate with the Golden LEAF Biomanufacturing Training and Education Center (BTEC) the cGLP production of the prebiotics galacto-oligosaccharides (GOS) and GOS enriched in N-acetyl-D-lactosamine (LacNac, humanized GOS, hGOS) for the clinical intervention planned for the study. BTEC has the capabilities, equipment, and expertise for the bioprocess cGLP production (See Appendix 1).

Formulation/Packaging/Labeling: GOS, hGOS, and placebo will be supplied as a sterile powder by BTEC, dried and portioned into daily dose pouches under sterile conditions at the NC Food Innovation Lab, Kannapolis, NC, . Pouches will be labeled and will serve to protect the preparations from light, air,

Protocol Number:
Study Acronym: GOS Pilot

Enrollment ID:

Lot No.:

Subject Number:

Subject's Initials:

Date Dispensed:

Contents: 56 pouches, 5 g each for the first 10 days followed by 7.5 grams each for days 11-28 of GOS, hGOS or matching placebo, plus two additional packets (one 5mg and one 7.5mg) for inadvertent loss or spillage.

Directions: Use only as directed. To be taken by mouth with food or beverage.

This product is an investigational product to be dispensed only by a qualified investigator.

Storage: Room Temperature 15-30 °C (59-86°F)

Caution: New drug limited by law to investigational (clinical trial) use only. Keep out of reach of Children.

Manufactured By: Golden LEAF Biomanufacturing Training and Education Center (BTEC), [name]

Distributed by:

and moisture. Product will then be transferred to the UNC Investigational Drug Services (IDS).

Storage and Stability:

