The powder prebiotics galacto-oligosaccharides (GOS), GOS enriched in N-acetyl-D-lactosamine (LacNac, humanized GOS, hGOS), and placebo can be safely stored in a dry area at room temperature and hold an expiration date of 2 years after production.

Preparation and Administration: Individuals will be provided with a total of 58 pouches numbered by day (#1 to #56) containing the appropriate daily dose of treatment or placebo. Pouches 57 and 58 will be extra pouches in case of loss or spillage. Participants will be instructed to consume one pouch twice a day. The premeasured powder can be added to hot or cold non-alcoholic beverages or sprinkled over food.

Modification: Individuals experiencing more than three of the following side effects a day: bloating, flatulence, belching, abdominal pain, discomfort, watery stool, and vomiting will be instructed on how to spread out the daily dose to minimize side effects. Participants experiencing these side effects be asked about frequency and severity. Severe side effects interfering significantly with subject's usual function will result in withdrawal from study. Weekly phone contacts will allow for timely report of adverse effects. Participants will also be given the choice to contact the study PI directly in case of emergencies.

Accountability: UNC Investigational Drug Services (IDS) will keep source documentation for accountability of the study treatments that will detail receipt, dispensing, and return of used and unused prebiotics and placebo. Treatment products will be stored in locked facilities until they are either returned to the PI at the end of the study. Prior to dispensing, sachets containing the treatment will be visually inspected. If the package appears to have tears or sign of tampering, the sachet will be rejected for use but retained until the end of the study. At the end of the study, the study team will determine dispensation of all remaining unused treatment packs at the study site. An accountability log will be kept, indicating the final disposition of study treatment. This log will be provided to the PI at the end of the study.

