10.1. Risk / Benefit Assessment

Potential Risks: Subjects in the GOS and hGOS groups will consume 7.5-15g/day of the prebiotics or placebo preparations as a drink. Possible side effects of the GOS and hGOS groups may include mild to moderate bloating, gas (flatulence), belching, abdominal pain or discomfort, and vomiting. Individuals will be withdrawn from the study if treatment leads to severe side effects.

Potential Benefits: Substances defined as "prebiotics" (a substrate that is selectively utilized by host microorganisms conferring a health benefit per the latest definition of the International Scientific Association for Probiotics and Prebiotics, ISAPP) have a demonstrated beneficial effect in humans and animals. Galacto-oligosaccharides (GOS) in particular have been shown to alleviate symptoms of lactose intolerance and other minor gastrointestinal manifestations in adequate doses.

A compromised gut barrier, dysbiosis and inflammation are hallmarks of the aging gut with consequences that can range from mild GI manifestations like constipation, abdominal pain, and flatulence, to disorders of the gut-brain axis and other conditions not directly associated with the GI tract. This study will add to the knowledge of beneficial modulation of the microbiota to mediate restoration of the gut barrier and biomarkers of inflammation. A positive outcome from

this study will further advance research to improve nutritional conditions and overall health of older individuals in long-term care.

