10.2. Assessment of Safety

Participants will be withdrawn if during the first 10 days of study participation, they experience a 2 level change in one or more of the most reported side effects (bloating, flatulence, watery stools, abdominal pain as assessed by questions 2 (abdominal pain), 6 (abdominal discomfort), 8 (constipation), 16 (diarrhea), 22 (abdominal distention), 26 (abdominal bloating), 31 (nausea), or 33 (vomiting) on the PROMIS Gastrointestinal Symptom Scale as compared to their baseline responses. Participants who have surpassed 10 days of study participation and experience a 2 level change in one or more of the most reported side effects (as described above) as compared to baseline, they will be asked to reduce the dose of study product to one sachet of 7.5 mg per day. The study product can be taken all at once or distributed between two time points. If the PROMIS Gastrointestinal Symptom Scale does not improve upon reducing the dose, the participant will be withdrawn from the study. If 5 or more of the first 20 subjects enrolled experience a 2 level change in the most commonly reported side effects (bloating, flatulence, watery stools, abdominal pain) compared to baseline or higher adverse event leading to subject discontinuation, we will stop the study temporarily and request the medical monitor to do an unblinded assessment of the data. The medical monitor (unblinded) will assess subjects who discontinued due to the specified adverse effects to determine if they are all in one arm of the study or range across arms. The medical monitor will assess if there is a safety signal in a specific arm or treatment dose over the other that warrants the closure of the study. Since the medical monitor will be the person determining continuation or discontinuation of the study, the study team will remain blinded and unbiased.

Participants who choose to withdraw from the study will be followed up (via text or email communication) to determine safety and efficacy outcomes. Reasons for discontinuation will be documented in the study RedCap database.

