10.4. Safety Monitoring

Investigators will assess subjects at each visit and over the phone or via text (or email) each week of the study at days 0, 7±2, 14±2, 21±2, and 28±2 as well as day 7±2 post-intervention. If AEs as defined in this protocol are identified (a 2 level change in one or more of the symptoms as compared to baseline as assessed by questions 2 (abdominal pain), 6 (abdominal discomfort), 8 (constipation), 16 (diarrhea), 22 (abdominal distention), 26 (abdominal bloating), 31 (nausea), or 33 (vomiting) on the PROMIS

Gastrointestinal Symptom Scale). The treatment will be first be reduced to one 7.5g sachet per day (taken either at once or divided between two time periods if the participant has been participating for \geq 10 days. The treatment will be discontinued if the participant is in the first 10 days of participation, and the AE will be recorded. Also, participants who report severe side effects (interfering significantly with subject's usual function) will be withdrawn from the study immediately. If 5 or more of the first 20 subjects enrolled experience a 2 level change in the most reported side effects (bloating, flatulence, watery stools, abdominal pain as assessed by questions 2 (abdominal pain), 6 (abdominal discomfort), 8 (constipation), 16 (diarrhea), 22 (abdominal distention), 26 (abdominal bloating), 31 (nausea), or 33 (vomiting) on the PROMIS Gastrointestinal Symptom Scale compared to baseline or higher adverse event leading to subject discontinuation, we will stop the study temporarily and request the medical monitor to do an unblinded assessment of the data.

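### After day 10 the same symptom trigger leads to 5 g twice daily in section 6.7 but one 7.5 g sachet a day in sections 10.2 and 10.4, and the dispensed kit does not cover the 6.7 dose

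*Combined protocol and SAP*

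**What the plan says.** Section 4.1 sets the regimen at 5 g twice daily on days 1–10 and 7.5 g twice daily on days 11–28. Three sections then say what to do if, past day 10, a participant moves two levels from baseline on PROMIS questions 2, 6, 8, 16, 22, 26, 31 or 33:

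- **Section 6.7:** the participant is "asked to go back to the lower dose of 5g sachets twice daily and reassessed in 3 days". On retention: "If participants are able to tolerate the lower dose, they will continue participating in the trial".
- **Section 10.2:** "they will be asked to reduce the dose of study product to one sachet of 7.5 mg per day". On retention: "If the PROMIS Gastrointestinal Symptom Scale does not improve upon reducing the dose, the participant will be withdrawn from the study". No time for that judgement is given.
- **Section 10.4:** "The treatment will be first be reduced to one 7.5g sachet per day". It gives no separate reassessment step after the reduction.

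On supply, section 6.1 says "Individuals will be provided with a total of 58 pouches numbered by day (#1 to #56"), with pouches 57 and 58 as spares. Section 6.3 describes the spares as one 5 g and one 7.5 g pouch. Section 7.4 hands over all 28 days of product at Visit 1. Sections 7.5 to 7.7 list no later dispensing.

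**The concern.** Specific Aim 1 is to validate the safety and tolerability of 15 g/day. The step-down rule governs what happens when that dose is not tolerated, so it bears directly on the primary outcome. As written, two participants with the same event can receive different doses and different decisions about staying in, depending on which section the coordinator opens.

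This can reach the results in four ways:

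- Drop-out is a tolerability measure (section 8.1), so the retention rule can change a measured outcome.
- Section 7.8 leaves discontinued participants out of Objective 2, so the rule also affects who is analysed there.
- Adherence is self-reported pouches left (section 6.6). A step-down to one sachet a day leaves sachets over, which could look like non-adherence unless the step-down is recorded.
- Aim 1 in section 9.2 does not plan to report step-downs, so a reader could not separate tolerance of 15 g/day from tolerance of a reduced dose.

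**Working it through.** **1. Are the orders compatible?** The eight items and the two-level threshold are the same in all three sections.

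| | 6.7 | 10.2 | 10.4 |
|---|---|---|---|
| Reduced dose | 2 × 5 g = 10 g/day | one sachet, 7.5 with unit mg | one sachet, 7.5 g/day |
| Share of 15 g/day | 10/15 = 67% | 50% if g is meant | 7.5/15 = 50% |
| Reassessment | in 3 days | no time given | none stated |
| Stays in if | lower dose tolerated | scale improves | not stated |

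No 7.5 mg sachet exists in the regimen, so the unit in 10.2 is a slip for g. The label text in 6.1 makes the same slip for the spares ("plus two additional packets (one 5mg and one 7.5mg) for inadvertent loss or spillage"), which 6.3 gives in grams. After correction, 10.2 and 10.4 agree on dose and 6.7 differs by 2.5 g/day, up to 2.5 × 18 = 45 g over days 11–28. On retention, a participant whose score is unchanged but bearable could stay under 6.7 and would be withdrawn under 10.2.

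**2. Kit contents (reproducing the plan's own count).** 5 g pouches: 2 × 10 = 20. 7.5 g pouches: 2 × 18 = 36. Total 20 + 36 = 56, plus two spares = 58, as section 6.1 states. With spares, that is 21 × 5 g and 37 × 7.5 g.

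**3. Can the kit supply each reduced dose?** Assume no missed dose, the spares unused and no resupply. The 5 g pouches left after day 10 are 21 − 20 = 1. If step-down starts on day *s*, the days left are 28 − *s* + 1. Section 6.7 needs two 5 g pouches a day and section 10.4 needs one 7.5 g sachet a day. The 7.5 g sachets on hand are 37 − 2 × (*s* − 11).

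| Step-down from | Days left | 5 g needed (6.7) | 5 g on hand | 7.5 g needed (10.4) | 7.5 g on hand |
|---|---|---|---|---|---|
| Day 11 (worst case) | 18 | 36 | 1 | 18 | 37 |
| Day 12 (start of second contact window) | 17 | 34 | 1 | 17 | 35 |
| Day 14 | 15 | 30 | 1 | 15 | 31 |
| Day 21 | 8 | 16 | 1 | 8 | 17 |

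The 3-day reassessment alone needs 3 × 2 = 6 of the 5 g pouches. The kit covers the 10.4 dose from any day and does not cover the 6.7 dose from any of these days.

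**4. Dose taken.**

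- Days 14–28 (15 days): 10 × 15 = 150 g under 6.7, 7.5 × 15 = 112.5 g under 10.4, against 15 × 15 = 225 g planned.
- Days 21–28 (8 days): 80 g or 60 g, against 120 g.
- Whole course planned: 10 × 10 + 15 × 18 = 370 g. With step-down from day 14: 100 + 45 + 150 = 295 g, or 100 + 45 + 112.5 = 257.5 g.

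**The case against.** The contradiction in dose cannot be disputed on the text. The strongest case is that it matters less than it seems.

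- **Both rules lower the dose, and severe effects lead to withdrawal under either.** The gap is 2.5 g/day, and 10 g/day has already been taken on days 1–10. This stands, and it limits the concern to inconsistent handling.
- **Aim 1 is descriptive, and section 10.4 counts the two-level change itself as an adverse event.** A triggering participant is therefore in the any-event figure under either rule. This also stands, but later events, drop-out and adherence can still differ. The plan gives no expected step-down rate, so the number affected is unknown.
- **Resupply is not described but not excluded, and missed pouches are set aside (section 4.1).** Some participants may hold a few extra 5 g pouches. This softens the supply point: the 6.7 dose is not provided for, rather than impossible. It does not touch the conflict between sections.
- **The wider text does not say which dose is meant.** Section 10.1 ("Subjects in the GOS and hGOS groups will consume 7.5-15g/day of the prebiotics or placebo preparations as a drink") fits 10.2 and 10.4, but the synopsis and sections 4 and 4.1 give 10–15 g/day, which fits 6.7. This is correct, so the choice of rule needs a decision and cannot be inferred.
- **Section 10.4 keeps weekly assessments, and section 9 says protocol departures will be documented.** Some follow-up and recording therefore exist. Neither supplies a common reassessment time or a plan to report step-downs.

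**Conclusion.** The plan is wrong as written and must be corrected. For one trigger it gives two reduced doses, 10 g/day and 7.5 g/day (67% and 50% of target), and retention rules that can disagree for the same participant. Following one section breaches another. This part rests on the text alone.

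The supply finding (1 pouch on hand against 6 for the reassessment and up to 36 to day 28) assumes full adherence on days 1–10, an unused spare and no resupply. The gram totals describe one participant, not an effect on a trial result. The same rule applies to all blinded arms, so no bias between arms is claimed.

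**What to change.** State one step-down rule once and refer to it from 6.7, 10.2 and 10.4. The sponsor and the medical monitor choose between:

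- **Option A:** one 7.5 g sachet a day. The kit already supports it. The 10–15 g/day wording in the synopsis and sections 4 and 4.1 should then acknowledge the lower step-down dose.
- **Option B:** 5 g twice daily, with the drug service holding up to 36 extra 5 g pouches per participant (35 if the spare is unused), issued only on step-down. The lower limit in 10.1 should then be 10 g/day.

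Under either option:

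- Set one reassessment time, for example 3 days, and one rule for withdrawing those who have not improved.
- Correct mg to g in 10.2 and on the label in 6.1.
- Record the date of each step-down, and report the number stepped down and the dose taken, by arm, under Aim 1.
- In the same amendment, say increase rather than change throughout, and replace the 10-or-more-days wording in 10.4 with after day 10. Also drop flatulence from the parenthetical symptom lists or add its item to the trigger.

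The cost is amendment wording in three sections, matching dose-range edits, a label correction and one reporting line. Option A needs no new product, Option B needs the extra pouches, and neither needs more participants or visits.

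### After day 10, the same PROMIS trigger leads to 5 g twice daily in section 6.7 but to one 7.5 g sachet a day in 10.2 and 10.4, and the documents describe no supply for the 6.7 dose

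*Combined protocol and SAP*

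**What the plan says.** Three sections tell staff what to do when any of the same eight PROMIS items (2, 6, 8, 16, 22, 26, 31, 33) rises 2 levels over baseline.

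- **Section 6.7.** Past day 10 the participant is "asked to go back to the lower dose of 5g sachets twice daily and reassessed in 3 days". It adds: "If participants are able to tolerate the lower dose, they will continue participating in the trial".
- **Section 10.2.** Past day 10, "they will be asked to reduce the dose of study product to one sachet of 7.5 mg per day", taken at once or split. Then: "If the PROMIS Gastrointestinal Symptom Scale does not improve upon reducing the dose, the participant will be withdrawn from the study". No time is set for that judgement.
- **Section 10.4.** "The treatment will be first be reduced to one 7.5g sachet per day", whole or divided, with the routine weekly contacts continuing.

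In the first 10 days the three agree that the participant stops.

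Section 6.1 describes the supply. The label reads "Contents: 56 pouches, 5 g each for the first 10 days followed by 7.5 grams each for days 11-28", and "Pouches 57 and 58 will be extra pouches in case of loss or spillage". Section 6.3 makes the extras one pouch of each size. Under 7.4, the packets for all 28 days are given at Visit 1. Under 4.1, a missed pouch is put aside and the next numbered pouch is taken.

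**The concern.** Staff cannot follow both 6.7 and 10.2/10.4, and the protocol states no order of precedence. The dose a symptomatic participant takes therefore depends on which page is open, and staff who follow 6.7 have no described source for the sachets it calls for.

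This is first a participant-safety instruction. It also touches the outcomes. Drop-out is a tolerability measure (4.3, 8.1), and under 7.8 a participant discontinued after Visit 1 counts for Objective 1 but not Objective 2. With 16 per arm, one participant is 1/16 = 6.25% of an arm. If the post-reduction check comes at different times for different participants, withdrawals may too.

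**Working it through.** **Inputs.** Regimen: 2 × 5 g on days 1-10, then 2 × 7.5 g on days 11-28 (4.1). Spares: one of each size (6.3). Contacts at days 14±2 and 21±2 (7.1). The sachet in 10.2 is taken as 7.5 g, because the only sizes made are 5 g and 7.5 g. The label in 6.1 makes the same mg slip for the spare packets, which 6.3 gives in grams.

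**The plan's own count reproduces.** 10 × 2 = 20 pouches of 5 g; 18 × 2 = 36 of 7.5 g; 20 + 36 = 56; with two spares, 58, as 6.1 states.

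**Dose conflict.** Section 6.7: 2 × 5 = 10 g/day, which is 10/15 = 67% of the target dose. Sections 10.2 and 10.4: 7.5 g/day, 7.5/15 = 50%. The gap is 2.5 g/day.

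**Supply at full adherence.** All 20 scheduled 5 g pouches are used by day 10, so one remains. Let the reduced dose start the day after a contact on day c and run for d = 28 − c days.

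- 5 g pouches needed under 6.7: 2d. Held: 1. Short: 2d − 1.
- 7.5 g sachets needed under 10.2/10.4: d. Held: 36 − 2(c − 10) + 1 = 2d + 1.

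| Contact day c | Days left d | 5 g needed | Short | 7.5 g needed | 7.5 g held |
|---|---|---|---|---|---|
| 12 | 16 | 32 | 31 | 16 | 33 |
| 14 | 14 | 28 | 27 | 14 | 29 |
| 16 | 12 | 24 | 23 | 12 | 25 |
| 19 | 9 | 18 | 17 | 9 | 19 |
| 21 | 7 | 14 | 13 | 7 | 15 |
| 23 | 5 | 10 | 9 | 5 | 11 |

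The 3-day check alone needs 3 × 2 = 6 pouches of 5 g, so it is short by 5.

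**Set-aside pouches.** They cover the 3-day check only if 5 of 20 (25%) were missed. After the day 21±2 contact, they reach day 28 only if 9 to 17 of 20 (45-85%) were missed. After the day 14±2 contact they cannot reach it: at most 20 + 1 = 21 pouches of 5 g are dispensed, below the 24-32 needed.

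**Product taken to day 28, 6.7 against 10.2/10.4.** After the day 14±2 contact: 120-160 g against 90-120 g. After the day 21±2 contact: 50-90 g against 37.5-67.5 g.

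**The case against.** The strongest reply is that 6.7 is one stray sentence. The 7.5-15 g/day range in 10.1, the rules in 10.2 and 10.4, and the kit all fit 7.5 g/day, so a sensible coordinator would use that. This stands as a guide to the repair. It does not remove the conflict, because the 10-15 g/day in the synopsis fits 6.7 instead.

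The investigational pharmacy also keeps dispensing records (6.1) and could issue more 5 g pouches. Resupply is indeed not ruled out. The supported statement is that no source is described, not that the dose could never be supplied.

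Some stronger readings might be inferred, and the documents do not support them:

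- *That 10.2 has no check after the reduction.* It has one: withdrawal if the scale does not improve. Only its time is missing.
- *That nothing is said about a participant who fails the lower dose.* Section 6.7 alone gives only the continuing branch, but 10.2 supplies withdrawal.
- *That the day-10 wording is a serious flaw.* Section 10.4 reduces the dose at 10 days or more, yet also says "The treatment will be discontinued if the participant is in the first 10 days of participation". The overlap is marginal: ten days can be read as completed, and no scheduled contact falls on day 10 (windows are days 5-9 and 12-16).
- *That the shortfall is 35 pouches.* That figure assumes a step-down on day 11, which needs an unscheduled report.
- *That the results will be biased.* No step-down rate is given. The triggering rise is an AE under 10.4 whichever dose follows, and 9.6 plans multiple imputation as a sensitivity analysis if data are missing at random.

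The dose-spreading advice in 6.1 has a different trigger and does not change the daily amount, so it does not settle the matter.

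**Conclusion.** The dosing rule is wrong as written. One event has two prescribed doses, 10 and 7.5 g/day, and only 6.7 gives a time for the check. For a fully adherent participant, 6.7 cannot be followed from the supply described: one 5 g pouch against 6 for the 3-day check, a shortfall of 23-31 to day 28 after the day 14±2 contact, and of 9-17 after the day 21±2 contact. The 7.5 g/day dose can be supplied throughout.

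This assumes that 10.2 means grams, that the reduction starts the day after the contact, and that no resupply occurs. The conflict between sections needs only the first of these. The effect on trial results is not estimated. The point should be corrected because it governs the handling of a symptomatic participant.

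**What to change.** Use one rule, in the same words, in 6.7, 10.2 and 10.4:

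> After day 10, if any listed PROMIS item is 2 levels above baseline, reduce to one 7.5 g sachet per day, whole or divided. Repeat PROMIS 3 days after the reduction, or at the final visit if sooner. Withdraw the participant if the scale does not improve.

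This replaces the twice-daily 5 g instruction in 6.7, corrects mg to g in 10.2, carries the 3-day check across, and keeps the withdrawal criterion that 10.2 already has. No new withdrawal threshold is needed. Keep the first-10-days rule and immediate withdrawal for severe effects. Footnote the 3-day contact in the Table of Events. Tabulating dose reductions by arm is optional.

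**Cost.** Wording in three sections, one footnote, and one extra contact per dose-reduced participant. The kit is unchanged. The downside is that 7.5 g/day lies below the synopsis range of 10-15 g/day, though within the 7.5-15 g/day in 10.1.

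**Alternative.** If the sponsor prefers 5 g twice daily, change 10.2 and 10.4 instead and describe a blinded resupply of 5 g pouches through the investigational pharmacy. For a reduction at a scheduled contact that is up to 31 pouches, or 31 × 5 = 155 g, per affected participant.
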